4.0 SYNOPSIS

Project title	INTERNATIONAL REGISTRY FOR AMBULATORY BLOOD PRESSURE AND ARTERIAL STIFFNESS TELEMONITORING
Project name	VASOTENS (Vascular health ASsessment Of The hypertENSive patients) REGISTRY
Scientific Coordinator	[name] (Italy) Clinical Research Unit Italian Institute of Telemedicine [name] Italy
Co-coordinator	[name] (Russia) [name] Hemodynamic Laboratory Nizhniy Novgorod Russia
Project centers	At least 30 Hypertension centers will be involved in the project, each one providing at least 100 patients, which will be followed-up over time. Centers will be selected in different countries, initially in Europe, starting from Italy and Russia. Mandatory criteria of a center to be included in the study are the availability in the facility of a BPLab ABPM monitor, the potential for providing and properly following-up the number of patients required by the protocol, the availability of Internet connection, regular access to the web and human resources to upload ABPM and clinical data.
Date of starting of the project	Launch of the project (first investigators' meeting): June 2015 First patient uploaded into the database: September 2015
Objectives	The project has several practical objectives and questions to be answered. These will be: 
 • The evaluation of non-invasive ambulatory blood pressure and arterial stiffness estimates (through pulse wave analysis, PWA) in hypertensive subjects undergoing an ambulatory blood pressure monitoring (ABPM) for clinical reasons in the selected centers • The evaluation of the changes in blood pressure and arterial stiffness estimates following treatment initiation according to current guidelines • The assessment of the impact of non-invasive arterial stiffness estimation on target organ damage and patient's cardiovascular (CV) prognosis • The definition of the normalcy thresholds for pulse wave velocity (PWV), augmentation index (AI), and other current and future indices derived from PWA in hypertensive subjects, according to outcome data • The definition of the relationship between arterial stiffness, blood pressure absolute level and blood pressure variability, and outcomes • The setup of a worldwide network of centers performing ambulatory PWA, and the validation and promotion of the use of such technique for hypertension screening and follow-up • The provision of evidence of the clinical relevance of non-invasive arterial stiffness assessment, in order to favor the inclusion of such evaluation in recommendations on hypertension management
Methodology	International, multicenter, observational, prospective project
Population	The registry will include data from subjects fulfilling the inclusion criteria and whose data are contained in existing databases collected by the participating centers and who are regularly followed-up at the center. New subjects can be enrolled for this project, but they must be submitted to ABPM because it is required for evaluating their hypertension status, according to current recommendations
Inclusion criteria	
 • Male and female subjects • Age ≥ 18 years • Subjects referred to routine diagnostic evaluation for hypertension or established hypertensive subjects • ABPM performed for clinical reasons with a BPLab device • The minimum validity requirements for inclusion of the ABPM in the study are: 
 – Interval between measurements not exceeding 30 minutes

	
 - At least 70% of expected number of readings - At least 20 valid readings during the day-time and 7 during the night-time • Availability of individual measurements for ABPM on a .bpw file (BPLab format) or data directly downloaded on the telemedicine platform of the study (see below for details) • Availability of basic demographic and clinical information: 
 - Age - Gender - Height - Weight - Ethnicity - Superficial distance between jugulum and symphysis (surrogate of aortic length) - Waist circumference - Smoking status - Alcohol drinking - Coffee or tea drinking - Dyslipidemia (yes/no and indication on treatment) - Diabetes (yes/no and indication on treatment) - Diagnosis of hypertension (yes/no and indication on treatment) - Family history of premature CV disease - Medical history, with particular regard to previous and/or concurrent CV diseases - Office blood pressure and heart rate obtained in the same treatment condition as ABPM - Left ventricular mass index (LVMI) at echocardiogram - When available, diameter of the aorta (aortic annulus, root and sinotubular junction) and/or cardiac output, assessed by the echocardiogram - Intima-media thickness (IMT) at carotid ultrasonography - ECG (indication on left ventricular hypertrophy, Sokolow–Lyon and Cornell index) - When available, ankle-brachial index - Microalbuminuria and serum creatinine (calculation of estimated glomerular filtration rate - eGFR) - When available, pulse wave velocity (PWV), augmentation index (AI) and central blood pressure taken during the office visit with a validated device different for BPLab Vasotens (e.g. Sphygmocor or Complior) • Availability of a signed informed consent form
Exclusion criteria	
 • Age <18 years • Atrial fibrillation, frequent ectopic beats, second or third degree atrioventricular blocks, or other conditions which might make difficult or unreliable the automatic blood pressure measurement with the oscillometric technique • Upper arm circumference <22 cm • Pregnancy
Data collection	
Data contained in existing electronic databases or data of newly enrolled subjects fulfilling the inclusion criteria will be uploaded/entered on the study website. These data will include ABPM measures (blood pressure and arterial stiffness) obtained with a BPLab device and clinical data. ABPM data will be provided as .bpw files or directly uploaded by linking the ABPM device to the website through a personal computer.
 
Data collection will be ensured by a dedicated web-based telemedicine platform, including an electronic case report form (e-CRF). The e-CRF will allow collection of patient’s clinical data, such as family history, anthropometric data, habits, past and current diseases, therapies, office BP, and laboratory tests, including evaluation of target organ damage.
 
The project does not involve any type of intervention related to the study and the physicians will manage the patients included in the Registry according to the requirements of clinical practice and current guidelines. However, as recommended by current guidelines, each patient will be followed-up with visits occurring at regular intervals (ideally every 6 months, and not less than once a year). The

	
physicians will also be free to use the ambulatory blood pressure data in the clinical management of the patients.
 
The telemedicine system will allow a) standardized and centralized data collection, b) data validation by experts and counselling to remote centers, c) setup and maintenance of the Registry.


Statistical methods
	
Standard variables (systolic and diastolic blood pressure, pulse pressure and heart rate), central systolic and diastolic blood pressure, and arterial stiffness indices (PWV and AI) will be averaged for the whole 24-hour period, and separately for the day-time and night-time subperiods. Additionally, hourly averages will be computed, and in case of blood pressure, variability will be evaluated by calculation of weighted standard deviation and average real variability.
 
Other variables of interest will be defined in the course of the study and calculated subsequently according to the procedures defined in a specific statistical analysis plan.
 
The occurrence of any CV event (death or hospitalization for congestive heart failure, myocardial infarction, angina, stroke or cerebrovascular accident, renal failure, etc.) during the study will be evaluated by the Kaplan-Meier method. Time-to-event curves will be drawn and the survival analysis will be performed according to the Cox proportional hazard model, which will allow to analyze predictors of outcomes. Relationship between blood pressure and arterial stiffness estimates and organ damage and prognosis will be evaluated.

5.0 LIST OF ABBREVIATIONS

ABPM	=	Ambulatory Blood Pressure Monitoring
AI	=	Augmentation Index
CRO	=	Contract Research Organization
CV	=	Cardiovascular
ECG	=	Electrocardiogram
e-CRF	=	electronic CRF
eGFR	=	Estimated Glomerular Filtration Rate
IMT	=	Intima Media Thickness
LVMi	=	Left Ventricular Mass Index
PWA	=	Pulse Wave Analysis
PWV	=	Pulse Wave Velocity

6.0 INTRODUCTION

In recent years, great emphasis has been placed on the role of arterial stiffness and central blood pressure as independent predictors for the development of cardiovascular (CV) diseases [1-3]. Consequently, the assessment of arterial stiffness and central hemodynamics is recommended as additional tests for the clinical evaluation of hypertensive patients (based on history, physical examination and findings from routine laboratory tests), particularly for those at risk for CV complications [4].

Regional and local arterial stiffness may be measured directly, and non-invasively, at various sites along the arterial tree, by assessing Pulse Wave Velocity (PWV) and Augmentation Index (AI) [1]. Central BPs are derived from non-invasive techniques of measurement of radial or carotid pulses [5].

The most widely employed methods for evaluating pulse waveforms are those based on applanation tonometry and transfer functions, although recently oscillometric ambulatory blood pressure monitoring (ABPM) devices using specific algorithms for pulse wave analyses (PWA) have been proposed for assessing arterial stiffness [6-9]. At present, oscillometry is an affordable technique, and may allow a comfortable, accurate, repeated and prolonged estimation of arterial stiffness and central hemodynamics over the 24-hours in daily life conditions [9]. The most recent studies seem to indicate reliability and feasibility of ambulatory arterial stiffness evaluation based on analysis of brachial oscillograms [10-12].

However, very few information is available on the prognostic value of ambulatory central blood pressure [13,14], and no information at all is provided by any study on the clinical value of 24-hour arterial stiffness estimation (PWV and AI). For this reason, we decided to create a large database (registry) of ABPM recordings obtained with a non-invasive device, able to determine central BP and various indices of arterial stiffness (mainly PWV and AI) over the 24-hours, based on a clinically validated technology of PWA of oscillometric BP measurements, integrated in the ambulatory BP monitor [10,12,13]. Specifically, this project aims at creating an international network of centers performing ABPM and arterial stiffness monitoring, in order to evaluate the impact of such estimates on the clinical outcome of hypertensive patients. The results of the data collected at baseline and during regular follow-up of hypertensive patients will help to provide evidence on the clinical usefulness of such technologies for the screening and follow-up of the hypertensive patients.

7.0 PROJECT OBJECTIVES

The specific project objectives are:

- The evaluation of non-invasive ambulatory blood pressure and arterial stiffness estimates (through PWA) in hypertensive subjects undergoing an ABPM for clinical reasons in the selected centers
- The evaluation of the changes in blood pressure and arterial stiffness estimates following treatment initiation according to current guidelines
- The assessment of the impact of non-invasive arterial stiffness estimation on target organ damage and patient's CV prognosis
- The definition of the normalcy thresholds for PWV, AI and other current and future indices derived from PWA, in hypertensive subjects, according to outcome data
- The definition of the relationship between arterial stiffness, blood pressure absolute level and blood pressure variability, and outcomes
- The setup of a worldwide network of centers performing ambulatory PWA, and the validation and promotion of the use of such technique for hypertension screening and follow-up
- The provision of evidence on the clinical relevance of non-invasive arterial stiffness assessment, in order to favor the inclusion of such evaluation in recommendations on hypertension management

8.0 OVERALL PROJECT DESIGN AND PLAN

International, multicenter, observational, prospective project

9.0 SELECTION OF PROJECT POPULATION

The registry will include data from subjects fulfilling the inclusion criteria and whose data are contained in

existing databases collected by the participating centers and who are regularly followed-up at the center. New subjects can be enrolled for this project, but they must be submitted to ABPM because it is required for evaluating their hypertension status, according to current recommendations.

While the present document contains the initial list of participating countries (Italy and Russia) and centers, other centers willing to participate in the project and able to provide a significant contribution may be accepted also after the project has initiated.

9.1 Inclusion criteria

- Male and female subjects
- Age ≥ 18 years
- Subjects referred to routine diagnostic evaluation for hypertension or established hypertensive subjects
- ABPM performed for clinical reasons with a BPLab device
- The minimum validity requirements for inclusion of the ABPM in the study are:
 - Interval between measurements not exceeding 30 minutes
 - At least 70% of expected number of readings
 - At least 20 valid readings during the day-time and 7 during the night-time
- Availability of individual measurements for ABPM on a .bpw file (BPLab format) or data directly downloaded on the telemedicine platform of the study (see below)
- Availability of basic clinical information (as detailed in Section 14.1):
- Availability of a signed informed consent form

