12.3 Investigators

This multicenter international project will involve investigators from Hypertension Centers worldwide. Initially two countries will be involved in the studies (Italy and Russia).

Basic technical requirements for the inclusion of a center in the project will be:

- The availability in the facility of a BPLab ABPM monitor
- The ability to perform proper 24-hour ABPM
- The potential for providing and properly following-up the number of patients required by the protocol
- The availability of Internet connection, regular access to the web and human resources to upload ABPM and clinical data

The investigator will need to have a medium-high level of expertise in informatics.

Given the observational nature of the project, it will not foresee any costs for the doctors and health insurance system and will not cause implementation of additional diagnostic examinations or changes in the use of any specific class of antihypertensive drugs.

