14.0 DATA MANAGEMENT

14.1 Electronic Case Report Form (e-CRF)

Data will be collected for each patient by an e-CRF located on a website. The e-CRF will allow the collection of the main demographic and clinical data including the patient's medical history and concomitant therapies. All data must accurately reflect the patients' view, or be an expression of their knowledge about their health.

The following data will be entered in the e-CRF, for each subject and visit:

- Age
- Gender
- Height
- Weight
- Ethnicity
- Superficial distance between jugulum and symphysis (surrogate of aortic length)
- Waist circumference
- Smoking status
- Alcohol drinking
- Coffee or tea drinking
- Dyslipidemia (yes/no and indication on treatment)
- Diabetes (yes/no and indication on treatment)
- Diagnosis of hypertension (yes/no and indication on treatment)
- Family history of premature CV disease
- Medical history, with particular regard to previous and/or concurrent CV diseases
- Office blood pressure and heart rate obtained in the same treatment condition as ABPM
- Left ventricular mass index (LVMI) at echocardiogram
- When available, diameter of the aorta (aortic annulus, root and sinotubular junction) and/or cardiac output, assessed by the echocardiogram
- Intima-media thickness (IMT) at carotid ultrasonography
- ECG (indication on left ventricular hypertrophy, Sokolow–Lyon and Cornell index)
- When available, ankle-brachial index

- Microalbuminuria and serum creatinine (calculation of estimated glomerular filtration rate - eGFR)
- When available, pulse wave velocity (PWV) augmentation index (AI) and central blood pressure taken during the office visit with a validated device different for BPLab Vasotens (e.g. Sphygmocor or Complior)

Access to the e-CRF will be granted through authentication with ID and password. The investigator will be responsible for the faithful transcription of the results of any laboratory or instrumental diagnostic tests. If changes have to be made to data, they will be overwritten with the correct ones. The system will keep record of the date and time of the corrections.

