## 2. DATA COLLECTION

Detailed study procedures and further information and details on the study are available in the study protocol.

Briefly, each center will enroll 100 patients from their pool of hypertensive patients. There are no specific inclusion criteria, except that:

- Patients must be at least 18 years-old
- Patients with frequent ectopic beats, including atrial fibrillation must be excluded
- Arm circumference must be at least 22 cm (appropriate cuff must be used in case of large arms)

Patients will be visited ideally at 6 month-intervals or once-a-year. During the visit they will be submitted to an ABPM and clinical data (see below) will be collected.

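### Protocol and SAP set different entry rules: the protocol requires echo, carotid, ECG and renal test results that the project says it will not generate, while the SAP's entry criteria require none of them

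*Protocol*

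**What the plan says.** **Protocol.** Section 9.1 lists "Availability of basic clinical information (as detailed in Section 14.1" among the inclusion criteria. The synopsis prints the whole list under its own inclusion criteria, introduced by "Availability of basic demographic and clinical information". Four test groups appear in Section 14.1 with no qualifier:

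- "Left ventricular mass index (LVMI) at echocardiogram"
- "Intima-media thickness (IMT) at carotid ultrasonography"
- "ECG (indication on left ventricular hypertrophy, Sokolow–Lyon and Cornell index"
- "Microalbuminuria and serum creatinine (calculation of estimated glomerular filtration rate - eGFR"

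Three other entries in the same list are marked as needed only when available: aortic diameter or cardiac output, ankle-brachial index, and office PWV/AI/central pressure from another device. Section 12.3 states that the project, being observational, "will not cause implementation of additional diagnostic examinations".

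**SAP.** Section 2 says "There are no specific inclusion criteria, except that" and then names only age, ectopic beats or atrial fibrillation, and arm circumference. Section 3 selects the analysis set on age and ABPM quality. Section 2.2 nevertheless asks for the full data list in the CRF, with the same split between qualified and unqualified items. Section 3.1 recodes a missing value to 0 for a set of variables that includes left ventricular hypertrophy on ECG.

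**The concern.** The two documents describe different populations. Take a patient with a valid ABPM and regular follow-up but no carotid scan. A site following the protocol must leave this patient out; a site following SAP 2 would enrol them. Case mix could then depend on which document a site follows.

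If the protocol rule is applied, two things are at stake. First, entry depends on having already had all four test groups. If testing in practice is related to organ damage, the enrolled patients differ from the hypertensive patients the registry means to describe. The relation between stiffness and organ damage, an objective in Protocol 7.0 and a main analysis in SAP 3, may then be affected. Second, the survival analysis in Protocol 11.0 and SAP 3 needs an ABPM and follow-up for events. It needs neither echo nor IMT, yet patients lacking them, and their events, would be lost.

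If the SAP rule is applied instead, patients with no ECG information are counted as free of ECG hypertrophy.

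**Working it through.** The plan gives no figure to reproduce, so the check is mainly a comparison of texts.

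**Step 1: is each test needed for entry?**

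| Item | Protocol synopsis, 9.1 and 14.1 | SAP 2 and SAP 3 entry/analysis criteria | SAP 2.2 CRF list |
|---|---|---|---|
| LVMI | required | not mentioned | required |
| Carotid IMT | required | not mentioned | required |
| ECG indices | required | not mentioned | required |
| Albuminuria, creatinine | required | not mentioned | required |
| Ankle-brachial index, aortic diameter | only when available | not mentioned | only when available |

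Because some items in the list carry the qualifier, the items without it read as required. With the statement in Protocol 12.3, a missing test would not be ordered to qualify a patient, so on the protocol's wording that patient cannot enter.

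**Step 2: what could this do?** The documents give no testing rates. Every input below is an assumption, used only to show the range.

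*Share qualifying.* If each test group is available in a fraction q of patients, independently, the share with all four is q^4: 0.5^4 = 6%, 0.7^4 = 24%, 0.9^4 = 66%. If the tests are always ordered together, the share is simply q, so 70% to 90% for the upper two values.

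*Observed prevalence of damage.* With true prevalence p and complete work-up in s1 of damaged and s0 of undamaged patients, the observed prevalence is p·s1 / [p·s1 + (1 − p)·s0]. For p = 0.30:

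- s1 = s0: 30%, no shift
- s1 = 0.6, s0 = 0.4: 0.18 / (0.18 + 0.28) = 39.1%
- s1 = 0.8, s0 = 0.4: 0.24 / (0.24 + 0.28) = 46.2%

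*Stiffness/organ-damage odds ratio.* Let s be the probability of complete work-up, with first index stiffness and second index damage. The odds ratio among those admitted is the true odds ratio × (s11·s00) / (s10·s01). For a true value of 2.0:

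| Work-up depends on | s11, s10, s01, s00 | Factor | Observed |
|---|---|---|---|
| damage only | 0.8, 0.4, 0.8, 0.4 | 1.0 | 2.0 |
| stiffness only | 0.8, 0.8, 0.4, 0.4 | 1.0 | 2.0 |
| both, multiplicatively | 0.8, 0.4, 0.4, 0.2 | 1.0 | 2.0 |
| both, additively | 0.9, 0.6, 0.6, 0.3 | 0.75 | 1.5 |
| either one suffices | 0.8, 0.8, 0.8, 0.4 | 0.5 | 1.0 |
| only both together | 0.8, 0.4, 0.4, 0.4 | 2.0 | 4.0 |

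The odds ratio moves only when work-up depends on both factors and not multiplicatively.

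**Step 3: the recode.** If a fraction m of ECG results is missing, unrelated to hypertrophy, setting them to 0 gives an observed prevalence of p(1 − m). For p = 20% this is 18%, 14% and 10% at m = 10%, 30% and 50%.

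**The case against.** The best defence is that the SAP does not compete with the protocol. SAP 2 offers its list as a brief summary, refers to the protocol for detail, and SAP 2.2 wants the same data. Requiring organ-damage data in a registry with an organ-damage objective is a defensible choice that buys completeness. Centres are hypertension clinics; if they work up patients uniformly, selection on suspected damage would be small. Protocol 14.2 lets investigators be asked to complete missing data. The SAP 3.1 recode names only ECG hypertrophy among the disputed tests, and because data are collected at every visit, gaps at later visits are compatible with an entry condition.

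Much of this stands. A reader might infer that the registry will in fact admit only worked-up patients and that its organ-damage results are therefore biased. The documents do not support that. The SAP's criteria would admit the others, neither document says that testing follows suspected damage, and Step 2 shows that the odds ratio need not move. Adjustment for confounders, planned in SAP 3, might also remove part of any effect.

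Two things are not answered. SAP 2 denies having further criteria, and the SAP 3 analysis set also omits the tests, so the conflict is more than a matter of summary. And patients kept out never contribute PWV, covariates or events, so the selection cannot be measured from registry data. Sites keep a file of patients assessed but not included (Protocol 14.2), but no analysis of it is planned.

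**Conclusion.** The entry rule is contradictory and should be reconciled. On the protocol's wording, four test groups are entry conditions and the project will not generate them; on the SAP's wording, none is an entry condition. The protocol rule may select patients already worked up, and it removes patients and events from a survival analysis that does not need these tests. These conclusions rest on the texts alone, except that the number of patients and events lost depends on testing rates the documents do not give.

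The size and direction of any bias in the stiffness/organ-damage association cannot be determined from the documents. The range of 1.0 to 4.0 around a true odds ratio of 2.0, the prevalence shifts and the 6% to 66% qualifying share all come from assumed inputs, and the last also assumes that the tests are independent. They show that the effect could be nil or material and do not estimate it. The effect of the ECG recode has a definite direction: setting unknown results to 0 can only lower the recorded prevalence or leave it unchanged.

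**What to change.** - Write one eligibility rule and use it in the protocol synopsis, Protocol 9.1 and 14.1, and SAP 2, 2.2 and 3. Mark LVMI, IMT, ECG indices and albuminuria/creatinine as needed only when available in routine care, as is already done for ankle-brachial index and aortic diameter.
- Keep every patient with a valid ABPM in the event analysis, whether or not these tests were done.
- Analyse each type of organ damage only in patients tested for it, and remove ECG hypertrophy from the variables recoded to 0 in SAP 3.1.
- Report how many patients lack each test, and compare tested with untested patients, including by PWV level. This is needed because per-test analysis reduces selection by testing but does not remove it.

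The change is to wording and analysis specification and adds no tests. Its cost is more missing organ-damage values and a separate denominator for each organ-damage analysis.
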